### 10.1 Imaging companion study incorporated within A091105: Evaluation of MRI T2 signal as a novel imaging biomarker in DT/DF treated with sorafenib

#### 10.1.1 Objectives

In a retrospective study, DT/DF patients treated with sorafenib demonstrated decrease in MRI T2 signal intensity suggesting a decrease in cellularity. In this prospective trial, we will undertake exploratory studies to test whether MRI T2 changes can predict (or correlate) with a biological response such as RECIST response, and pain palliation (for patients whose disease is being monitored by MRI).

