**Decision Rule:** We will randomize a total of 75 patients (25-placebo, 50-sorafenib) and observe patients until we have reached 52 PFS events for the efficacy analysis. In the event the median PFS in the control group is larger than expected and long-term follow-up becomes a concern, we will perform the final efficacy analysis after 52 events are observed or after all evaluable patients have been followed for at least 3 years, whichever occurs earlier. If the 1-sided p-value associated with the Log-Rank test is  $< 0.0255$  (corresponding to an observed HR of 0.5776), we will consider sorafenib as having shown promising activity in this population and may recommend it for further testing.

**Inefficacy/Futility Analysis:** We will evaluate the observed PFS of the arms when 45% of the PFS events required for the final efficacy analysis (i.e., 24) have been observed.

We will terminate the study for futility if the p-value associated with the test statistic from a Log-Rank is at least 0.5025 (corresponding to an observed HR of 1.0027). Otherwise, we will continue to complete full enrollment.

Although the primary endpoint will be evaluated using the first 75 evaluable patients, final efficacy results will further report results (e.g., publication, presentation) using all patients evaluable for determining PFS and so that patient enrolled beyond these 75 may contribute to these estimates.

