### 15.1.2 Maximum Accrual

Maximum accrual is 83 patients, which includes 10% over accrual to replace those patients deemed ineligible due to improper histology having been determined on the basis of information available prior to randomization.

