### 15.3 Correlative Companion Study Endpoints

#### 15.3.1 Statistical design- Imaging study

About 50% (38 patients) are expected to have extra-abdominal disease and be evaluated by MRI. Percent change in tumor size by RECIST and percent changes in MRI T2 signal will be calculated at baseline and at response evaluation every 8 weeks. Best RECIST response (ordinal variable) and percent T2 signal change (continuous) will be correlated by Spearman's rho. Careful attention will be paid to patients having received sorafenib after PD on the placebo arm, which may involve censoring or adjusting the patient baseline at the initiation of sorafenib. The percent changes in MRI T2 signal from Week 8 to subsequent imaging will be compared between groups with >30% pain palliation using t-test or a nonparametric alternative (e.g., Wilcoxon rank-sum test). Data, analyses, and censoring will also follow the note described in [Section 15.2](#).

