#### 15.3.2 Statistical design- A091105-H01, QOL study

Pain palliation will be defined at each time point as  $\geq 30\%$  decrease from baseline in the worst pain intensity score (BPI-SF "worst pain" item), with neither a concomitant  $\geq 30\%$  increase in average daily use of any opioid narcotic, nor addition of any new opioid narcotic, relative to baseline.

A patient must meet the criteria for pain palliation at both Week 8 and Week 12 to be considered a responder for the primary endpoint. The primary statistical analysis will include all eligible and consented patients who provide baseline pain and pain medication data, have a baseline pain level greater than or equal to 3, and who initiate treatment. Any patient who does not provide pain and pain medication data at Week 8 and Week 12 will be considered a non-responder (i.e., a "failure" for the endpoint but will be included in the denominator).

Pain progression at a given time point is defined as a  $\geq 30\%$  increase compared with baseline in the worst pain intensity score (BPI-SF "worst pain" item) or either a  $\geq 30\%$  increase in the average daily use of any type of opioid narcotic or the addition of a new opioid narcotic compared with baseline. Time to pain progression is defined as the date of randomization to the earliest date that pain progression is observed. Patients not reporting pain progression will be censored at their date of last pain and pain medication data reporting. Time to pain palliation is defined as the date of randomization to the earliest date that confirmed pain palliation is observed. Duration of pain palliation is defined for all patients who experience confirmed pain palliation and is the time from the earliest date that confirmed pain palliation is observed to the earliest date that pain progression is observed. Patients not reporting pain progression will be censored at their date of last pain and pain medication data reporting.

For the primary analysis, the rate of pain palliation at Week 8 confirmed as Week 12 will be compared between arms using a two-sided  $\alpha=0.05$  chi-squared tests at the time of the final analysis.

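### Section 15.3.1 relates T2 change to pain only through a 30% palliation cut; adding one rank correlation beside it would recover about 8 to 14 points of power under moderate assumed correlations

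*Combined protocol and SAP*

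**What the plan says.** Section 10.1.1 describes the imaging work as exploratory and sets out to "test whether MRI T2 changes can predict (or correlate) with a biological response such as RECIST response, and pain palliation". Objective 2.3.1 is worded similarly.

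Section 15.3.1 gives two analyses. For tumour response, "percent T2 signal change (continuous) will be correlated by Spearman's rho", paired with best RECIST response as an ordinal variable. For pain, percent T2 change "will be compared between groups with >30% pain palliation using t-test or a nonparametric alternative (e.g., Wilcoxon rank-sum test". The section names only one group; the natural reading is patients with palliation against patients without. It states no power, effect size, correlation or alpha. On sample size it says: "About 50% (38 patients) are expected to have extra-abdominal disease and be evaluated by MRI".

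Section 15.3.2 defines palliation at each time point as a fall of at least 30%, a "decrease from baseline in the worst pain intensity score (BPI-SF 'worst pain' item), with neither a concomitant" rise of 30% or more in any opioid nor a newly added opioid. It is therefore a composite of percent change and an opioid rule.

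Section 6.2 has HO1 patients complete the BPI at baseline and every 4 weeks to Week 32. Section 7.0 schedules scans every 8 weeks for the first 3 years. Section 7.0 requires the worst-pain item of all patients before registration, but later pain scores come only from HO1, which is optional and restricted to English speakers (Sections 5.4.1 and 6.2).

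**The concern.** An aim phrased as predicting or correlating invites the question of whether larger T2 loss goes with larger pain relief. The planned comparison cannot answer it. A 35% fall in worst pain counts the same as a 100% fall, and a 25% fall counts the same as a worsening. The scores needed for a graded analysis are already collected in HO1, and the same section already uses a rank correlation for RECIST.

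At stake is the only specified test of the T2-pain relation, in a small sample. Section 1.10 makes this relation important: it reports symptomatic improvement with T2 change but without RECIST response, and hypothesises that T2 signal predicts clinical benefit in stable disease. A real association would be missed more often than necessary.

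**Working it through.** **Sample size.** Section 15.1.1: "We will randomize a total of 75 patients (25-placebo, 50-sorafenib"). Half of 75 is 37.5, which reproduces the stated 38. Section 15.1.2: "Maximum accrual is 83 patients"; half of that is 41.5, so 38 is an expectation and not a ceiling. The usable number is probably smaller. Section 15.3.2 bases its primary pain analysis on 51 patients, and 38 × 51/75 = 25.8, or about 26.

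**Responder share.** Section 15.3.2 assumes 50% palliation on sorafenib and 10% on placebo. At 2:1 the pooled share is (2/3)(50%) + (1/3)(10%) = 36.7%. This gives about 14 against 24 patients at n = 38, and about 10 against 16 at n = 26.

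**Assumptions not in the documents.** The T2-pain correlation (rho) was taken as 0.2 to 0.6. Two-sided alpha was 0.05; Section 15.3.2 uses 0.05 and Section 15.3.1 states none.

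**Large-sample efficiency.** Under bivariate normality, splitting one variable at responder share q keeps φ(z_q)²/[q(1 − q)] of the information in a Pearson correlation. This is 0.64 at q = 0.50, 0.61 at 0.37 and 0.54 at 0.25.

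**Power on the integer pain scale.** T2 change and latent percent pain change were bivariate normal. Baseline worst pain was an integer, uniform on 3 to 10, and the follow-up score was rounded and clipped to 0 to 10. Palliation was a fall of at least 30%, with no opioid effect. There were 3,000 replicates per cell, so the Monte Carlo error of a power near 50% is √(0.5 × 0.5/3,000) = 0.9 points.

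| n | rho | t-test by palliation | Spearman | Difference (points) |
|---|---|---|---|---|
| 38 | 0.4 | 50% | 64% | 14 |
| 38 | 0.5 | 71% | 85% | 14 |
| 38 | 0.6 | 87% | 96% | 9 |
| 26 | 0.4 | 35% | 46% | 11 |
| 26 | 0.5 | 54% | 68% | 14 |
| 26 | 0.6 | 71% | 86% | 15 |

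A repeat at n = 38 gave 50% v 63%, 71% v 85% and 88% v 96%, that is 13, 14 and 8 points. At n = 26 the loss is about 12 to 14 points, give or take the simulation error. With rho = 0, rejection rates were 0.051 to 0.058 for the t-test and 0.045 to 0.048 for Spearman.

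**Sensitivity to rho and responder share.** A separate simulation without rounding of scores (20,000 replicates, n = 38, 37% share) gave 49% v 66%, 71% v 87% and 88% v 97% at rho 0.4, 0.5 and 0.6. At rho 0.2 it gave 16% v 21%, a loss of about 5 points. With a 25% share and rho 0.4 to 0.6, the loss against Spearman was 15 to 23 points.

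**Sensitivity to opioid use.** The runs above do not let added opioids lower the reported score. When 20% to 30% of patients escalate, preferentially those with worse pain, and this lowers reported pain by 60% of baseline, the advantage disappears or reverses. At n = 38 and rho 0.4, one run gave 48% for the t-test and 44% to 45% for Spearman. With the worst 30% escalating, another gave 47% and 39%. With a 40% lowering, a gain of about 6 to 14 points remained; that figure depends on the assumed pattern of escalation.

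**The case against.** The strongest reply is that the objective names palliation, and palliation in this protocol is a responder status that is primary in HO1. Comparing T2 change by that status tests the stated objective with the trial's own endpoint. It also guards against the case where pain falls because opioids rose. That stands, and it is why the comparison should stay. A reader might infer that it should be replaced or demoted; the documents do not support that, because percent change in worst pain is a different construct and omits opioid use.

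Three other stronger readings are tempting.

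- That the plan cuts the raw 0-10 score. It does not: the cut is on percent change, joined to the opioid rule.
- That the loss is a fixed quantity in a sample capped at 38. The documents give no T2-pain correlation and no responder share for the MRI cohort, and 38 is only an expected number.
- That a stated power or a trial conclusion is wrong. The work is exploratory, and Section 15.3.1 makes no power claim and sets no decision rule.

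It is also fair that MRI and HO1 assessments coincide at up to four visits (Weeks 8, 16, 24 and 32). A correlation with no named visit would add several looks, so the visit must be fixed in advance.

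What remains is narrower. Nothing in the plan relates T2 change to the degree of pain relief, and under moderate correlations with little opioid distortion the cut loses power that data already collected could recover.

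**Conclusion.** The concern holds as a case for a cheap addition, not as an error in the plan. With rho 0.4 to 0.6, about 37% responders, two-sided alpha of 0.05 and no opioid effect on reported pain, the palliation split costs about 8 to 14 points of power against Spearman at n = 38, and about 12 to 14 points at n = 26. The loss is about 5 points at rho 0.2 and larger when responders are fewer. It can vanish or reverse if many patients raise opioids and this strongly lowers their reported pain. The correlation therefore belongs beside the palliation comparison. Apart from power, it addresses the graded question that the correlation aim raises and the two-group comparison cannot answer.

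**What to change.** In Section 15.3.1, keep the comparison of T2 change by palliation status, which carries the opioid rule. Alongside it, add a Spearman correlation between percent T2 change and percent change from baseline in BPI worst pain:

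- **Visit:** one visit named in advance where MRI and HO1 coincide, for example Week 8, with both changes taken from baseline. The existing comparison takes T2 change from Week 8 onward, so the text must state the baseline reference explicitly.
- **Population:** HO1 patients with MRI and baseline worst pain of at least 3.
- **Opioids:** flag patients who meet the opioid-increase or new-opioid condition on the scatter plot, and repeat the correlation without them as a sensitivity analysis.

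The same edit can name the two comparison groups and the palliation time point, and align the strict 30% threshold in Section 15.3.1 with the at-least-30% definition in Section 15.3.2.

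The cost is a sentence or two and one or two extra exploratory analyses on data already collected, with no new patients or visits. The main drawback is that the raw score does not reflect opioid changes, which the retained palliation comparison covers. The sensitivity analysis also selects patients on post-baseline behaviour, so it should be read only as a check.

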#### 15.3.2 Statistical design- A091105-H01, QOL study

Pain palliation will be defined at each time point as  $\geq 30\%$  decrease from baseline in the worst pain intensity score (BPI-SF "worst pain" item), with neither a concomitant  $\geq 30\%$  increase in average daily use of any opioid narcotic, nor addition of any new opioid narcotic, relative to baseline.

A patient must meet the criteria for pain palliation at both Week 8 and Week 12 to be considered a responder for the primary endpoint. The primary statistical analysis will include all eligible and consented patients who provide baseline pain and pain medication data, have a baseline pain level greater than or equal to 3, and who initiate treatment. Any patient who does not provide pain and pain medication data at Week 8 and Week 12 will be considered a non-responder (i.e., a "failure" for the endpoint but will be included in the denominator).

Pain progression at a given time point is defined as a  $\geq 30\%$  increase compared with baseline in the worst pain intensity score (BPI-SF "worst pain" item) or either a  $\geq 30\%$  increase in the average daily use of any type of opioid narcotic or the addition of a new opioid narcotic compared with baseline. Time to pain progression is defined as the date of randomization to the earliest date that pain progression is observed. Patients not reporting pain progression will be censored at their date of last pain and pain medication data reporting. Time to pain palliation is defined as the date of randomization to the earliest date that confirmed pain palliation is observed. Duration of pain palliation is defined for all patients who experience confirmed pain palliation and is the time from the earliest date that confirmed pain palliation is observed to the earliest date that pain progression is observed. Patients not reporting pain progression will be censored at their date of last pain and pain medication data reporting.

For the primary analysis, the rate of pain palliation at Week 8 confirmed as Week 12 will be compared between arms using a two-sided  $\alpha=0.05$  chi-squared tests at the time of the final analysis.

For the exploratory hypotheses, median time to pain palliation, duration of response, and time to pain progression will be estimated for each arm using Kaplan-Meier estimates and will be compared between arms using a log-rank test. All other items/questionnaires will be scored according to published scoring guidelines and statistical analysis will include all eligible and consented patients who provide data for the given outcome and who initiate treatment (i.e., the requirement for baseline pain to be  $\geq 3$  is not in effect for the other outcomes). Descriptive statistics will include means, standard deviations, medians, and ranges for each continuous or ordinal scale/subscale/item by group at each time point. Descriptive graphical techniques will include mean plots by group for each continuous or

ordinal scale/subscale/item. Relative frequencies of responses for each ordinal item will also be generated at each time point by group.

Each patient-reported outcome will be compared between arms at each time point using two-sample t-tests followed by analysis of covariance adjusting for the baseline value at each time point. Finally, a linear mixed-effects model with random intercepts and slopes will also be used to compare each continuous/ordinal patient-reported outcome over time between arms. In these linear mixed-effects models, the post-baseline score is the modeled outcome and the predictors are the baseline score of the given patient-reported outcome, arm, time (treated as a continuous variable and measured at the planned week of assessment), and treatment-by-time interaction.

Missing data will be handled in a number of ways. Baseline patient/disease characteristics will be compared between patients who provide data and patients who have missing data for each endpoint. We will also graphically explore patterns of missing data. All analyses will be completed using all available data, followed by analyses completed using imputed data using the arm minimum followed by the arm maximum. Lastly, we will employ pattern mixture models for longitudinal analyses. Output from all analyses will be compared to assess the degree to which missing data impacts study results.

For all statistical analyses, p-values <0.05 will be considered statistically significant. For interpreting the clinical significance of effects, 0.2, 0.5, and 0.8 SD effects will be considered as small, moderate, and large based on Cohen throughout.

**Power:** We anticipate ~70% of eligible patients who initiate treatment will be evaluable for the primary analysis of this companion study. With 51 patients contributing data for the primary analysis, the primary analysis has 80% power to detect a 40% difference in the rate of pain palliation at Week 8 confirmed at Week 12 between arms (50% pain palliation in the sorafenib arm versus 10% in the placebo arm) using a two-sided alpha=0.05 chi-squared test. Power for a 45% difference (55% pain palliation in the sorafenib arm versus 10% in the placebo arm) is 87%. These power calculations assume 2:1 randomization. This power calculation conservatively assumes that 10% of patients in the placebo arm will experience a “placebo effect” such that patients report improvement in pain despite being treated with a placebo.

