• **Pain Medication Diary:** Daily reporting for 7 consecutive days via paper diary prior to randomization, every 4 weeks through Week 32 while on randomized treatment, and at end of randomized treatment. This pain medication diary will be used to quantify opioid narcotic use for computing pain palliation and pain progression.

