| Subject ID: _____                                                                                                                                                                                                                                                                                                                                                                                              |                                                                                                   |                             | Assessment Period: _____                                                                                                                                                                                                                                                                                                                                                                                                                                                          |                                       |                                       | Research Staff Signature: _____       |                                       |                                       | Date: _____                           |
| 
Study Site Staff: Prior to each 7-day period, write in pain medication names, routes, and strengths in the columns below.
 
 
List only one type of medication on each row. Include all medications the patient is taking for pain or that may alleviate pain symptoms
 
Please write in the dates where indicated (Month/Day/Year).
 
 |                                                                                                   |                             | 
Study Participant: Please record the number of units you have taken of each medication over the prior 24 hours. If you are wearing a patch, mark a “1” for every day the patch is worn.
 
During this 7-day period, if you start a new medication for pain or change the strength of the pills, write the new information on a new row. (Do not change the information about the medication you have already taken.)
 |                                       |                                       |                                       |                                       |                                       |                                       |

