**APPENDIX III- DRUGS WITH RISK OF TORSADES DE POINTES**

This list contains medications that are generally accepted (and documented in published data) as having an increased risk of QT prolongation and/or torsades de pointes. Concomitant administration of sorafenib and a medication on this list is **prohibited**.

| Generic Name | Brand Name     | Comments                                                      |
|---------------------|-----------------------|----------------------------------------------------------------------|
| Amiodarone          | Cordarone®, Pacerone® | Low risk torsades de pointes                                         |
| Arsenic trioxide    | Trisenox®             | Torsades de pointes                                                  |
| Bepridil            | Vasocor®              |                                                                      |
| Chloroquine         | Aralen®               |                                                                      |
| Chlorpromazine      | Thorazine®            |                                                                      |
| Cisapride           | Propulsid®            | Restricted availability in U.S.                                      |
| Clarithromycin      | Biaxin®               |                                                                      |
| Disopyramide        | Norpace®              | Torsades de pointes                                                  |
| Dofetilide          | Tikosyn®              | Torsades de pointes                                                  |
| Dolasetron          | Anzemet®              |                                                                      |
| Droperidol          | Inapsine®             | Torsades de pointes                                                  |
| Erythromycin        | Erythrocin®, E.E.S. ® | IV > PO                                                              |
| Halofantrine        | Halfan®               |                                                                      |
| Haloperidol         | Haldol®               | IV > PO, high doses increase QT prolongation and torsades de pointes |
| Ibutilide           | Corvert®              | Torsades de pointes, female > male, non-Caucasian > Caucasian        |

|              |                                 |                                                                     |

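### The opioid clauses of pain palliation and progression test each drug separately, with no total dose and no rule for replacement, so a patient whose total opioid use falls can be scored as worse.

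*Combined protocol and SAP*

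**What the plan says.** Section 15.3.2 defines palliation at a visit as a fall of at least 30% in worst pain with neither a 30% or greater "increase in average daily use of any opioid narcotic, nor addition of any new opioid narcotic, relative to baseline". To be a responder, a patient has to satisfy this at Week 8 and again at Week 12. Pain progression is a 30% or greater rise in worst pain, or a 30% or greater "increase in the average daily use of any type of opioid narcotic or the addition of a new opioid narcotic compared with baseline". The *or* makes the opioid trigger sufficient whatever the pain score. Duration of palliation ends at pain progression, so it inherits the same rule.

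Section 10.2.2 names the data source: "This pain medication diary will be used to quantify opioid narcotic use for computing pain palliation and pain progression". The diary form has one medication per row, with its route and strength, and tells the patient: "Please record the number of units you have taken of each medication over the prior 24 hours". For patches it adds: "If you are wearing a patch, mark a “1” for every day the patch is worn". A new row is requested only for a new pain medication or a changed pill strength.

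No section defines average daily use as units or milligrams, sums it over drugs, converts it to a common opioid scale, or says how a replacement is to be scored.

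**The concern.** The opioid clause exists so that a fall in pain bought with more opioid is not counted as benefit. That purpose concerns how much opioid the patient takes in total. A rule applied drug by drug can give the opposite answer: total intake falls, one drug rises, and the patient is classed as a palliation failure and as a progression event.

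Pain palliation is the primary objective of A091105-HO1 (Section 10.2.1). Response must hold at both Week 8 and Week 12, so one mis-scored visit removes a responder. Time to pain progression and duration of palliation are also affected. Opioid adjustment is plausible in this population: the third eligibility route in Section 4.4 admits symptomatic patients on the basis of a recent narcotic increase or a new opioid.

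The patch instruction is a different fault that feeds the same endpoints. It can conceal a real increase.

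**Working it through.** **1. Two opioids, rebalanced.** Let the minor drug make up a share m of baseline use on a common scale, with m below one half. The main drug is halved and the minor one rises by half.

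- Change in total = −0.5(1 − m) + 0.5m = m − 0.5, which is negative for every m < 0.5.
- Illustration: main drug 60 → 30, minor drug 20 → 30. The total goes 80 → 60, or (60 − 80)/80 = −25%. The minor drug alone is up (30 − 20)/20 = +50%.
- Under Section 15.3.2 read drug by drug, +50% exceeds 30%. Palliation is blocked and progression is called, even if worst pain has fallen by 30% or more.

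**2. One opioid replaces another.** Illustration: drug A at 60, later drug B at 40, on a common scale.

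- Change in total = (40 − 60)/60 = −33%.
- B was not taken at baseline. If *addition* includes replacement, the new-opioid trigger fires, and it does so even if the 30% clause is read as a total. If *addition* means only a drug taken on top of the others, it does not fire. The text does not settle which.

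**3. A second identical patch.** The instruction gives an entry of 1 before and 1 after: recorded change 0%, true change (2 − 1)/1 = +100%. It is neither a new drug nor a changed pill strength, so neither opioid trigger fires. The worst-pain item may still detect worsening.

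**4. The stated power.** Inputs from Section 15.3.2: 51 patients, 2:1 (34 sorafenib, 17 placebo), 50% vs 10%, two-sided 0.05, chi-squared test. The plan does not name its power formula. The noncentral chi-squared with 1 df has

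λ = N · (1/3)(2/3) · (p_S − p_P)² / [p̄(1 − p̄)], with p̄ = (2p_S + p_P)/3.

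- 50% vs 10%: p̄ = 0.3667; λ = 51 × 0.2222 × 0.16 / 0.2322 = 7.81; power 79.8% (stated 80%).
- 55% vs 10%: p̄ = 0.40; λ = 51 × 0.2222 × 0.2025 / 0.24 = 9.56; power 87.1% (stated 87%).

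One formula reproduces both stated figures, so it is used below.

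**5. Sensitivity to lost responders.** The documents give no rate of switching or rebalancing. Assume that 30% to 50% of analysed patients take opioids, that 10% to 20% of those switch or rebalance by Week 12, and that every true responder among them is wrongly failed. The loss is then 0.30 × 0.10 = 3% to 0.50 × 0.20 = 10% of true responders. The last column is the power of the uncorrected chi-squared test by exact enumeration, with the loss in both arms.

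| Loss | Rates, loss in both arms | λ | Power | Power, loss in sorafenib arm only | Exact enumeration |
|---|---|---|---|---|---|
| 0% | 50.0% vs 10.0% | 7.81 | 79.8% | 79.8% | 86.4% |
| 3% | 48.5% vs 9.7% | 7.45 | 77.9% | 77.2% | 84.4% |
| 5% | 47.5% vs 9.5% | 7.21 | 76.6% | 75.4% | 83.0% |
| 10% | 45.0% vs 9.0% | 6.64 | 73.2% | 70.5% | 79.3% |

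The sorafenib-only column uses the same formula with placebo held at 10%; at 10% loss, for example, p̄ = 0.3333 and λ = 51 × 0.2222 × 0.1225 / 0.2222 = 6.25.

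**The case against.** **The wording can be read more kindly.** Adding is not replacing, and use of any type of opioid could mean opioids of whatever type, taken together. This stands in part: the one-for-one switch is a problem only if *addition* covers replacement. The kinder reading still leaves switches and the unit of use undefined, and the rebalancing example holds on the plain drug-by-drug reading.

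**The rule is deliberate.** Section 4.4 uses nearly the same construct for eligibility. A total-dose rule also has a blind spot: adding a second opioid with a total rise of 25% would no longer count. Both points are fair, and they are reasons to show both versions.

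**The effect is small and assumed.** True. The assumed loss is also an upper figure, since switchers whose total really rose by 30% or more are rightly failed. By exact enumeration the planned test keeps about 79% power even at a 10% loss.

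**Stronger readings that the documents do not support:**

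- A reader might infer that the protocol itself forces a scored switch, because Appendix III says "Concomitant administration of sorafenib and a medication on this list is" prohibited, and methadone is listed. But Section 4.2.4 already bars drugs with torsades risk at eligibility, and Section 6.2 places the baseline diary before treatment rather than before randomization. A scored switch needs a baseline diary completed while still on methadone. Section 10.2.2, which does place the diary before randomization, leaves that possible, but the case is narrow.
- A reader might blame the patch error on drug-by-drug scoring. It comes from the diary instruction and would corrupt a total-dose rule equally. Some patients may also follow the general instruction and write 2.
- A reader might infer that the error is equal in the two arms and always pulls toward no difference. Nothing in the documents establishes that.

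**Conclusion.** The concern holds as a weakness of definition. Section 15.3.2 can score a patient with less pain and less total opioid as a palliation failure and a progression event. This is certain for rebalancing under the plain reading, and conditional on the meaning of *addition* for a one-for-one switch. The patch instruction is a separate recording fault.

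The size is modest and rests on assumed rates. A 3% to 10% loss of true responders in both arms takes power from 79.8% to between 77.9% and 73.2%. No size can be given for time to pain progression, duration of palliation or the escalation hidden by patches. The point concerns an optional substudy and does not touch the progression-free survival analysis.

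**What to change.** **Definition.** Opioid use is the 7-day average total daily opioid dose: units × strength × a conversion factor fixed before the analysis, summed over all opioid rows of the diary. The opioid clause is met when that total is at least 30% above baseline, or when a patient taking no opioid at baseline starts one. A replacement without a 30% or greater rise in the total is not worsening.

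**Status.** Sections 14.1 and 15.1 record that patients were unblinded on November 17, 2017 after release of study data. Replacing the responder definition now would be a post-unblinding change. Keep the stated definition as primary for data already collected, and write down before analysis how *addition* and average daily use are applied. Specify the total-dose version as a labelled sensitivity analysis for palliation, time to pain progression and duration of palliation, and report both.

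**Diary.** For any further collection, record the number and strength of patches worn. In existing data, flag patch users as not resolvable on this point.

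**Cost.** Analysis wording, a conversion table and one extra set of analyses. Apart from patches, the names, strengths and counts are already in the diary. Conversion factors are approximate, and the sensitivity version will not count a second opioid that raises the total by less than 30%.
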